Clinicians can choose any attachment design whether it be the optimized attachments Invisalign provides, a horizontal attachment, or a beveled horizontal attachment, to name a few. A recent study found that orthodontists most frequently chose optimized (17%), rectangular (12%), incisally beveled rectangular (11%) or gingivally beveled rectangular attachments (46%) over other options for enhancing extrusion and that these choices were significantly different from those of general dentists (50%, 22%, 11%, and 3%, respectively). It is up to the clinician, using their expertise, to determine which attachment design best suits the goals of their treatment plan and there are no scientific data currently available. There are a limited number of prospective clinical studies in the literature on any aspects of orthodontic treatment using aligners.

2. * Describe the study hypothesis and/or research questions. Use lay language whenever possible.

Question: Which attachment design is most efficacious in extruding maxillary lateral incisor?

Null Hypothesis: There will be no difference in the efficacy among the four most-commonly used attachment designs (optimized, horizontal, gingivally-beveled horizontal, and incisally-beveled horizontal extrusion attachments) in extrusion of maxillary lateral incisor.

The goal of the study is to evaluate efficacy of different attachments and not their effectiveness on lateral incisor extrusion.

3. * Describe the study's specific aims or goals. Use lay language whenever possible.

The aim of this prospective, randomized controlled trial is to determine which of the four different attachment designs (optimized, horizontal, gingivally-beveled or incisally-beveled) offers more predictable extrusion of maxillary lateral incisors in patients treated with clear aligners (Invisalign, Align Technologies, Inc, USA). The secondary objective is to evaluate the accuracy of ClinCheck software in predicting the three-dimensional final position of the lateral incisor following extrusion using the attachment designs tested. The purpose is to be able to provide clinically-relevant recommendations for attachment planning for extrusion of maxillary lateral incisors during aligner treatment.

4. * Describe the scientific benefit or importance of the knowledge to be gained:

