Based on data from prior publications, the common standard deviation for extrusion was assumed to be 1.25. When the sample size is 15, a one-way repeated measures analysis of variance with a 0.05 significance level will have 80% power to detect a difference in means across the 4 groups of the repeated measures factor characterized by an effect size of 0.199 (based on a Variance of means, $V = \frac{(\sigma^2 - \rho^2)}{M}$, of 0.156, a standard deviation at each level of 1.25, and a between level correlation, ρ , of 0.5).

Increasing the sample size to 20 per group would have power to detect an effect size of 0.146 and variance of means of 0.114. These estimates reflect small effect sizes 15 and therefore would be able to detect clinically meaningful differences in the extrusion of the 4 attachments. Sample size calculations estimated with nQuery v8.5.2 (Statistical Solutions Ltd 2020).

4. * List the study inclusion criteria:

- (1) Patients 16 years or older to be treated with either Comprehensive Invisalign or Invisalign Teen,
- (2) Maxillary lateral incisor requiring 0.3 mm or more extrusion (as determined by ClinCheck),
- (3) Maxillary arch with less than 6 mm of crowding or spacing,
- (4) All teeth present and fully erupted (excluding third molars).

5. * List the study exclusion criteria:

- (1) Presence of anterior crossbite
- (2) Any missing teeth in the maxillary arch
- (3) Treatment plan includes surgery or extraction of any maxillary teeth,
- (4) Maxillary lateral incisors with pathology or large restorations (crowns)
- (5) Maxillary lateral incisors have a less than 0.3 mm of extrusion prescribed in the Tooth Movement Table on the Invisalign ClinCheck

6. * Will individuals with limited English proficiency be included in or excluded from this research?

Included

- Excluded - safety concerns if participants are unable to communicate with the study team
- Excluded - instruments/measures only validated in English
- Excluded - no prospect of direct benefit to individual participants
- Excluded - minimal risk study
- Excluded - lack of budget/resources for translation and interpretation [provide an explanation in next question]
- Excluded - other reason [provide an explanation in next question]

7. Justify the inclusion and exclusion criteria if you are either targeting, or excluding, a particular segment of the population / community. Provide a description of the group/organization/community and provide a rationale.

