During the scheduled appointment for the delivery of aligners, the patients will be instructed on how to properly place and remove aligners and their maintenance. Patients will be instructed to wear each aligner for a minimum of 22 hours a day for 7 days. Participants will verbally confirm compliance at each appointment. At the end of a series of 20-25 aligners, another intraoral scan will be taken and sent to Align Technologies to determine the final positions of the teeth. Comparison of initial and final positions (using Geomagic software) will be done to assess the efficacy of different types of attachments in lateral incisor extrusion.

Once the teeth are in desired positions, the treating orthodontist will remove the attachment (<6 months).

3.

Research related interventions include:

- a. random assignment of the specific type of attachment on lateral incisor;
- b. treating orthodontist placing the corresponding order in the prescription with Align Technology;
- c. delivery of attachments and aligners to the study participants
- d. Superimposition of final and initial positions of lateral incisors: Two superimpositions will be completed. The pretreatment model will be superimposed with the predicted final model to establish the predicted movement of the maxillary lateral incisors. The pretreatment model will be superimposed with the posttreatment model to establish the actual movement of the maxillary lateral incisor. The actual and predicted movement values will be calculated by the GeoMagic software. The amount of extrusion for the lateral incisors will be analyzed in increments of 0.1 mm.

Sample size: 80 maxillary lateral incisors with at least 20 teeth per study group. Randomization will occur at the level of individual lateral incisor tooth.

Study Duration: Patients will be evaluated only after the first series of aligners (20-25). Each set of aligners would be worn for a week and the study would span 20 - 25 weeks.

7. * The IRB only reviews research activities, so indicate which of the study activities are:

- **Being performed exclusively for research purposes (i.e. they would not otherwise be done apart from this study) VERSUS.**
- **Alterations of routine activities/procedures (e.g. the study is altering the timing, frequency, method, location, amount, etc.) VERSUS.**

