- **Being done for other purposes and whose data/results will be used secondarily in the study (e.g. standard medical or psychological tests, routine education practices, quality improvement initiatives, etc.).**

Research related interventions include:

- a. random assignment of the specific type of attachment on lateral incisor;
- b. treating orthodontist placing the corresponding order in the prescription with Align Technology;
- c. delivery of attachments and aligners to the study participants
- d. Superimposition of final and initial positions of lateral incisors: Two superimpositions will be completed. The pretreatment model will be superimposed with the predicted final model to establish the predicted movement of the maxillary lateral incisors. The pretreatment model will be superimposed with the posttreatment model to establish the actual movement of the maxillary lateral incisor. The actual and predicted movement values will be calculated by the GeoMagic software. The amount of extrusion for the lateral incisors will be analyzed in increments of 0.1 mm.

In clinical practice (as in this study) it is nearly always needed to take an intraoral scan at the end of the first set of aligners. This is an optical scanning of the mouth and has no additional risks associated with it. In this study, the scan will be used to assess the results of the randomized intervention. For practice purposes, it is used to construct retainers (if the treatment is done) or, more commonly, to construct an additional set of aligners to continue treatment and improve the result for the patient.

8. If applicable, describe alternatives (research or non-research) that are available to potential participants if they choose not to participate in this study:

They can choose to continue to receive the Invisalign care without being a part of the study. They will not be randomized and the treating orthodontist will choose the type of attachment based on clinical judgment and experience.

9. Upload any supporting tables or documents (e.g. protocol documents, figures/tables, data collection forms, study communications/reminders):

Upload ALL instruments/guides that will be used or that participants will experience (i.e. see, hear, complete), including measures, scripts/questions to guide interviews, surveys, questionnaires, observational guides, etc.:

Upload ALL recruitment and screening materials, including such as ads, flyers, telephone or in-person scripts,

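### The extrusion prescribed for each tooth should be a prespecified covariate in the attachment comparison; the plan gives it no stated role

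*Combined protocol and SAP*

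**What the plan says.** All places are in the combined protocol and SAP.

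- **Comparison.** Study Procedures, item 6: "Comparison of initial and final positions (using Geomagic software) will be done to assess the efficacy of different types of attachments". Extrusion is to be analysed in steps of 0.1 mm.
- **Model.** The only named analysis is in the sample-size paragraph (Study Population, item 3): "a one-way repeated measures analysis of variance with a 0.05 significance level". No covariate is mentioned. The same paragraph says "the common standard deviation for extrusion was assumed to be 1.25", without a unit.
- **Prescription.** The inclusion criteria require at least 0.3 mm of extrusion on ClinCheck and state no upper limit. The matching exclusion reads "Maxillary lateral incisors have a less than 0.3 mm of extrusion prescribed in the Tooth Movement Table on the Invisalign ClinCheck". Study Procedures, item 4, says ClinCheck gives the required movement in tenths of a millimetre and that final inclusion waits for its report.
- **Aim.** Background, Rationale and Goals, item 3, asks which design "offers more predictable extrusion of maxillary lateral incisors in patients treated with clear aligners". The secondary objective is to "evaluate the accuracy of ClinCheck software in predicting the three-dimensional final position of the lateral incisor".
- **Superimpositions.** Study Procedures, items 6 and 7: "The actual and predicted movement values will be calculated by the GeoMagic software".
- **Order of events.** Study Procedures, item 4, takes consent before the ClinCheck report. Item 6 triggers assignment when a participant has been recruited. Data Confidentiality and Storage, item 9, and Non-VCU Site Details, item 2, name consent as the step before assignment.

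**The concern.** Teeth enter with different prescriptions, and a tooth asked to move further will probably move further. That spread inflates the error term of a comparison based on achieved movement alone, and with 20 teeth per attachment the arms can differ in mean prescription by chance. A baseline value that predicts the outcome and is already on file is a natural covariate.

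The form of adjustment also matters. The prescription could be ignored, subtracted (achieved minus predicted) or used as a covariate, and the plan does not say which. Subtraction assumes that each extra prescribed millimetre yields a full extra millimetre. If teeth deliver less than half of it, subtraction adds noise. A covariate estimates the slope from the data.

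A covariate should be fixed before the arm is known. The attachment order goes to the manufacturer after assignment, so the predicted final model used in the superimposition could postdate assignment. The table value that decided eligibility is the safer choice.

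**Working it through.** **1. The plan's own figures.** Inputs from Study Population, item 3: SD 1.25, correlation 0.5, four levels, alpha 0.05. Effect size = V / [SD²(1 − ρ)], noncentrality λ = n × 4 × effect size, degrees of freedom 3 and 3(n − 1).

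- n = 15, V = 0.156: effect size 0.156 / 0.78125 = 0.1997, λ = 11.98, power 80.0%.
- n = 20, V = 0.114: effect size 0.114 / 0.78125 = 0.1459, λ = 11.67, power 79.98%.

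The stated figures (0.199 and 0.146 for 80% power) reproduce.

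**2. Reference case.** Randomisation is by tooth, with 80 teeth and 20 per attachment, so the comparison of methods uses four parallel arms of independent teeth. λ = 80 × 0.114 / 1.5625 = 5.84, df 3 and 76, power 48.3%. This serves only as a common baseline; its distance from 80% is a separate matter.

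**3. Assumptions.** The SD of 1.25 is taken as millimetres. The prescription SD (SDx) is set at 0.3, 0.5 and 1.0 mm. The slope of achieved on prescribed extrusion is set at 0.296, 0.5 and 1. The value 0.296 borrows the 29.6% accuracy for extrusion in Background, item 1; an accuracy is not a regression slope, so it is illustrative. Slope 1 is treated as an upper bound.

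**4. Formulas.**

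- Covariate: r = slope × SDx / 1.25; λ = 5.84 / (1 − r²), divided by 1 + 1/74 for expected chance imbalance in the covariate; df 3 and 75.
- Subtraction (predicted taken as equal to prescribed): variance = 1.5625 + SDx²(1 − 2 × slope); λ = 80 × 0.114 / variance; df 3 and 76.

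**5. Power (%), against 48.3 unadjusted.**

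| Slope | SDx (mm) | r | Covariate | Subtraction |
|---|---|---|---|---|
| 0.296 | 0.3 | 0.071 | 48.0 | 47.4 |
| 0.296 | 0.5 | 0.118 | 48.3 | 45.7 |
| 0.296 | 1.0 | 0.237 | 50.2 | 39.2 |
| 0.5 | 0.3 | 0.12 | 48.4 | 48.3 |
| 0.5 | 0.5 | 0.20 | 49.5 | 48.3 |
| 0.5 | 1.0 | 0.40 | 55.5 | 48.3 |
| 1 | 0.3 | 0.24 | 50.3 | 50.9 |
| 1 | 0.5 | 0.40 | 55.5 | 56.2 |
| 1 | 1.0 | 0.80 | 92.0 | 92.4 |

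The largest gain of the covariate over subtraction is 50.2 − 39.2 = 11.0 points. Its largest loss to subtraction is about 0.7 points, at slope 1.

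**6. Cost if the prescription is useless (r = 0).** λ = 5.84 / (1 + 1/74), df 3 and 75: power 47.7%, a loss of 0.6 points. In the plan's repeated measures form (error df 57 to 56) the loss is from 79.98% to 79.1%.

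**7. Type I error.** In a simulation of independent teeth (20,000 runs per setting, r from 0 to 0.7), the unadjusted and covariate-adjusted tests both rejected in 4.9 to 5.2% of null trials.

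**8. Chance imbalance.** The 95% range of the shift in a two-arm difference is ±1.96 × slope × SDx × √(2/20). For SDx of 0.3 to 1.0 mm this is ±0.06 to ±0.18 mm at slope 0.296, and at most ±0.19 to ±0.62 mm at slope 1.

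**9. Same contrasts on either scale.** If achieved = arm effect + b × prescribed + error, then achieved − prescribed = arm effect + (b − 1) × prescribed + error. With the prescription in the model, the attachment contrasts are identical for both outcomes.

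**The case against.** The strongest reply is that the benefit is undocumented. At the illustrative slope the covariate moves power by −0.4 to +1.9 points, and the large figures need slope 1 and SDx 1.0 mm together. That stands: the gain cannot be claimed in advance. What can be shown is that the possible loss is under 1 point.

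A second reply is that the covariate is not always the better method. That also stands. It loses slightly to subtraction at slope 1, and slightly to no adjustment when the prescription hardly predicts the outcome.

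Third, the aim speaks of predictability and both superimpositions are measured, so an achieved-versus-predicted comparison may be intended and a one-line outcome definition might suffice. The definition is needed. It does not displace the covariate, because the adjusted contrasts are the same on either scale, and unadjusted subtraction is the form that can cost power.

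Two stronger readings are tempting. A reader might infer that omitting the prescription biases the comparison; randomisation prevents that. A reader might also infer that the plan contradicts itself on whether assignment precedes the ClinCheck report. The documents do not support this. Non-VCU Site Details, item 2, makes recruitment depend on meeting the eligibility criteria, which include the ClinCheck threshold. Study Procedures, item 6, triggers assignment on recruitment and randomises individual teeth, which presupposes knowing which teeth qualify. The coherent order is consent, ClinCheck report, final inclusion, assignment. The wording is loose, not contradictory.

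**Conclusion.** The point holds as a matter of efficiency and prespecification, of modest weight. The public text gives the prescription no stated role in the attachment comparison, although it is known for each tooth before final inclusion. Under the assumptions in the working (SD in mm, independent teeth, V = 0.114, SDx 0.3 to 1.0 mm), the covariate ranges from a loss of under 1 point to an upper-bound gain of about 44 points over no adjustment (92.0 − 48.3, at slope 1 and SDx 1.0 mm). Against subtraction it ranges from about −0.7 to +11 points. Where the trial falls in these ranges is unknown. The figures do not evaluate a model with a patient term, and absence is judged on the public text, from which some pages were removed.

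**What to change.** 1. Analyse achieved extrusion (mm) across the four attachments with prescribed extrusion as a prespecified covariate, and a patient term where one patient contributes two teeth.
2. Define the covariate as the Tooth Movement Table value that decided eligibility, recorded for each tooth before the assignment is released.
3. Report achieved minus predicted by attachment alongside, and say whether predicted means that table value or the Geomagic superimposition.
4. State explicitly that assignment is released only after the ClinCheck value is recorded, and align Data Confidentiality and Storage, item 9, and Non-VCU Site Details, item 2, with this.

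Cost: one degree of freedom for the covariate, under 1 power point at worst, a few sentences and a little more analysis. No extra scan is needed, because final inclusion already waits for the ClinCheck report.

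### The aim is more predictable extrusion, but the stated comparison of designs is on amount of extrusion and does not relate achieved to predicted movement

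*Combined protocol and SAP*

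**What the plan says.** Background, Rationale and Goals (question 3), repeated in Study Procedures (question 2), gives the aim: to determine which of four designs "offers more predictable extrusion of maxillary lateral incisors in patients treated with clear aligners". The null hypothesis is worded differently: "There will be no difference in the efficacy among the four most-commonly used attachment designs".

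Study Procedures (question 6) gives the comparison of designs: "Comparison of initial and final positions (using Geomagic software) will be done to assess the efficacy of different types of attachments in lateral incisor extrusion". The same answer plans two superimpositions, pretreatment on predicted and pretreatment on posttreatment. It then says: "The actual and predicted movement values will be calculated by the GeoMagic software". The next sentence is: "The amount of extrusion for the lateral incisors will be analyzed in increments of 0.1 mm".

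Study Population (question 3) describes a one-way repeated-measures analysis of variance that "will have 80% power to detect a difference in means across the 4 groups of the repeated measures factor".

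The secondary objective comes closest to linking the two movements: "The secondary objective is to evaluate the accuracy of ClinCheck software in predicting the three-dimensional final position of the lateral incisor", under the designs tested. It gives no measure and no test by design. The application states that there is no separate protocol document, and it has no statistical analysis section.

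**The concern.** Predictability is about how near a tooth comes to its planned position, and how reliably. The initial-to-final change alone does not contain the planned position. Two teeth that each extrude 0.5 mm count the same, even if one was prescribed 0.5 mm and the other 1.5 mm.

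Prescriptions start at 0.3 mm with no stated ceiling, so their spread enters raw amount directly. Randomisation prevents systematic bias from this, but leaves noise and chance imbalance in arms of 20 teeth. A comparison of mean amounts also says nothing about consistency, and the power calculation assumes one common SD for all four designs.

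The trial could therefore report no difference, or recommend a design as more predictable, without testing predictability, although the data to test it will have been collected. With no measure named in advance, the choice could also be made after the results are seen.

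**Working it through.** **1. The plan's own figure.** Inputs from Study Population (question 3): SD 1.25, correlation ρ = 0.5, M = 4 levels, 5% level. Effect size = V / [SD²(1 − ρ)], noncentrality λ = n × M × effect size, with 3 and 3(n − 1) degrees of freedom.

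- n = 15, V = 0.156: 0.156 / (1.5625 × 0.5) = 0.1997; λ = 60 × 0.1997 = 11.98; power 80.0%.
- n = 20, V = 0.114: 0.114 / 0.78125 = 0.1459; λ = 80 × 0.1459 = 11.67; power 80.0%.

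The figures reproduce, taking the repeated-measures layout as given. They are for a difference in mean extrusion.

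**2. What the prescription costs.** The documents give no SD for actual minus predicted and no distribution of prescriptions, so these inputs are assumed. There are 20 independent teeth per design. Prescriptions are normal with mean 1.0 mm and SD 0.5 mm, and values below 0.3 mm are set to 0.3 mm, which reduces the SD to about 0.465 mm. One design falls short by 0.3 mm on average and three by 0.7 mm.

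Variance of the four means: V = (1/4)(3/4)(0.4)² = 0.03. For independent groups, λ = 80 × 0.03 / variance = 2.4 / variance.

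- Signed error, SD 0.3: λ = 2.4 / 0.09 = 26.7.
- Raw amount, SD 0.3: λ = 2.4 / (0.09 + 0.216) = 7.8.
- Signed error, SD 0.4: λ = 2.4 / 0.16 = 15.0.
- Raw amount, SD 0.4: λ = 2.4 / (0.16 + 0.216) = 6.4.

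**3. Simulated rejection rates at 5%.** The first three tests are one-way analyses of variance. The spread test is Brown-Forsythe on actual minus predicted. In the equal-mean rows, one design has error SD 0.3 mm and three have 0.6 mm. Ranges reflect separate simulation runs.

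| Scenario (assumed) | Raw amount | Signed error | Absolute error | Spread |
|---|---|---|---|---|
| Shortfall 0.3 v 0.7 mm, SD 0.3 | 61% | 99% | 99% | 3% |
| Shortfall 0.3 v 0.7 mm, SD 0.4 | 52% | 90% | 79–81% | 4% |
| Equal means, error centred on 0 | 5% | 6% | 71% | 61–62% |
| Equal means, shortfall 0.3 mm | 5% | 6% | 31–32% | 61% |
| Equal means, shortfall 0.5 mm | 5% | 6% | 11–13% | 61–62% |
| Equal means, shortfall 0.7 mm | 5% | 6% | 7% | 62% |

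The first two rows show what is lost by leaving the prediction out. The other four show that no comparison of means, signed or raw, detects a difference in consistency. Absolute error detects it well only when errors centre near zero. Under a common shortfall it is close to signed error with the sign reversed.

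**The case against.** The strongest reply is that the plan is underspecified, not wrong. It has no analysis section. The comparison of means is inferred from the sample-size answer, and the 0.1 mm sentence may be about resolution. The null hypothesis speaks of efficacy, which a comparison of amounts fits. The background uses predictability in the sense of achieved against anticipated movement, citing a mean accuracy of 41%, so a mean of achieved relative to predicted would be a legitimate reading of the aim. All of this stands. It does not make initial-to-final change a measure of predictability.

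Three stronger readings are tempting, but the documents do not support them.

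- *Over- and under-extrusion cancel, so an erratic design can tie with or beat a dependable one.* This needs errors on both sides of plan. The background describes shortfall: extrusion accuracy of 29.6%, and results still below those anticipated. It reports no over-extrusion. When errors run one way, a larger mean usually also means closer to plan.
- *Actual and predicted movement are never compared.* Both are derived for each tooth, and the secondary objective on ClinCheck accuracy implies a comparison. What is missing is a measure and a test by design.
- *Absolute error alone is the cure.* Under a common 0.5 mm shortfall it detects the SD 0.3 v 0.6 mm difference in only about 13% of trials.

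**Conclusion.** The concern holds in this form: the stated comparison of designs, on amount of extrusion, does not test the stated aim of more predictable extrusion, and the secondary accuracy objective does not define a measure or test that would.

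Under the assumed shortfalls of 0.3 v 0.7 mm, leaving out the prediction lowers the chance of detecting the difference from 90–99% (signed error) or 79–99% (absolute error) to 52–61% (raw amount). Under equal mean errors with SD 0.3 v 0.6 mm, tests of means stay at about 6% while a spread test reaches about 62%.

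These sizes rest on assumed SDs, an assumed prescription distribution and independent teeth. A narrower range of prescriptions would shrink the first gap. The mismatch between aim and comparison does not depend on these numbers.

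**What to change.** From the two superimpositions already planned, compute actual minus predicted extrusion for each tooth and compare the four designs on it, allowing for two teeth from one patient (for example with a patient random effect). Report three results by design:

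- signed error, which shows shortfall;
- absolute error;
- a comparison of spread, such as Brown-Forsythe.

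Before analysis, name one of these as the test of the predictability aim. Keep mean amount of extrusion as the efficacy result. State that the 80% power in Study Population (question 3) is for mean amount and does not apply to the chosen measure.

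The cost is wording only, with no new scans, visits or patients. The real downside is having to commit to one measure in advance, with power that is not the stated 80% and cannot be worked out from the documents because they give no SD for actual minus predicted.
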